### 7.3 LOST TO FOLLOW-UP

A patient will be considered lost to follow-up if he or she fails to appear for 3 intervention visits or return an assessment and study staff are unable to contact the participant after at least 3 attempts.

The following actions will be taken if a patient fails to return to the clinic for a required study visit:

- Staff will attempt to contact the participant, reschedule the missed intervention within 10 days, counsel the participant on the importance of maintaining the assigned visit schedule and determine if the participant wishes to and/or should continue in the study
- Before a participant is deemed lost to follow-up, the investigator or staff will make every effort to regain contact with the participant (where possible, 3 telephone calls and check-in at upcoming cancer care visit, and if necessary, a certified letter to the participant's last known mailing address). These contact attempts will be documented in the participant tracking log (Appendix J).
- Should the participant continue to be unreachable, he or she will be considered to have withdrawn from the study with a primary reason of lost to follow-up.

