#### Primary Objectives

1. To refine the Pathways intervention and study protocol based on acceptability feedback from an open pilot study (i.e., fully implement the intervention) with patient exit interviews ( $n = 6$ ). We will use feedback on the acceptability of session content, length, and delivery, and review intervention session recordings to refine the intervention. If necessary, we will refine the procedures for enrollment and retention.
2. To determine Pathways intervention feasibility in a single-arm pilot study ( $n = 55$  Pathways). Feasibility will be defined by enrollment ( $\geq 60\%$ ); primary feasibility outcome, retention ( $\geq 70\%$ ), adherence ( $\geq 70\%$  of patients completing 3 of 5 sessions), and mean acceptability ratings (scores of  $\geq 7$  out of 10 on intervention relevance, helpfulness, and convenience).

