**Inclusion of Women and Minorities.** Men and women of all races and ethnicities who meet the above-described eligibility criteria are eligible to participate in this study. We expect approximately 42% of participants to be women. Translating this to our sample size estimate of 61 (6 pilot; 55 single arm), we plan to enroll at least 25 women. We expect to enroll racially and ethnically diverse patients in proportions that reflect our catchment area: Hispanic/Latino (n = 1), Black or African American (n = 3), American Indian/Alaska Native (n = 1), and Asian (n = 1).

**Retention.** Patients will have up to 12 weeks (from the point of their first session) to complete Pathways. We will use previous retention strategies, including reminding patients of study visits, and offering sessions and assessments when they are in clinic for care. If they are hospitalized and want to participate, the study interventionist will meet them or resume upon discharge.

[figure not shown]
**Participant Compensation.** Patients in both Phase I and Phase II will receive a \$20 gift card for completing the baseline assessment and a \$30 gift card for completing the post-assessment. Patients in Phase I and II will receive an extra \$10 for completing the exit interview. Patients will receive gift cards upon completion of an assessment. Patients will receive the full gift card amount even if they elect to skip measures within an assessment, or, in the case of the exit interview, discontinue the interview.

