## 7 STUDY INTERVENTION DISCONTINUATION AND PARTICIPANT DISCONTINUATION/WITHDRAWAL

### 7.1 DISCONTINUATION OF STUDY INTERVENTION

If a patient discontinues the intervention, but not the study, remaining study procedures will be completed (e.g., post-assessment). Patients who discontinue the intervention will be asked to indicate the reason why they are discontinuing (e.g., intervention burden, decline in functional status, etc.; Appendix I). If a patient's post-assessment is due to be completed within 2 weeks of discontinuing the intervention, the post will be administered at the time of discontinuation. If the post assessment is scheduled for more than 2 weeks from the date they discontinue the intervention, the post assessment will be administered at the originally scheduled assessment.

Patients may be discontinued from the intervention by the investigative team if the study team or treating physician has concerns about the patient's mental status or psychological wellbeing, at which point procedures for managing patient safety and evaluating adverse events will be followed. The study will document reasons for discontinuing a patient (Appendix I).

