## 9.3 POPULATIONS FOR ANALYSES

The sample from phase I ( $n = 6$ ) will be used to refine procedures and the intervention protocol. The sample from phase II ( $n = 55$ ) will be used to analyze feasibility and acceptability data and describe pre-post changes in patient-reported outcomes.

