#### 9.4.2 ANALYSIS OF THE PRIMARY ENDPOINT(S)

The primary outcome of the feasibility is enrollment ( $\geq 60\%$ ). A one-sample binomial test will be used to compare the observed enrollment percentage to 60%.

Enrollment (primary): Number of patients enrolled divided by the number of eligible patients approached

Retention: The percentage of patients who complete baseline and post-treatment questionnaires

Adherence: The percentage of patients who complete at least 3 of 5 sessions in 10 weeks.

Acceptability: Mean post-treatment patient ratings  $\geq 7/10$  on intervention satisfaction (primary), convenience, helpfulness, relevance, recommendation to others, worth doing (0 = not at all to 10 = extremely); and a brief semi-structured interview to explore factors associated with acceptability

---

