## 13 AMENDMENT HISTORY

Version	Date	Description of Change	Brief Rationale
2	8/25/19	Added project members ([name], BCBR staff, CCTS staff); updated questionnaires and treatment information	Previous forms were rough drafts and missing information (e.g., treatment receipt items)
	11/25/2019	Added project members ([name], study nurse; [name], Program Manager; [name], CCTS regulatory)	
3	12/09/2019	Updated tracking forms, questionnaires, templates for participant postcard, magnet	Identified formatting changes that were needed to improve questionnaires. Identified formatting and minor changes needed to administrative tracking forms for study.
4	02/11/2020	Updated participant handouts, added [name], [name], and [name] to protocol, added CCTS Tableau for recruitment pre-screening	Identified formatting changes needed to improve patient materials. New study personnel (research assistants, study interventionist). Tableau through CCTS added to help

			reduce screening to potentially eligible patients
	10/23/2020	Removed [name], [name], and [name] from personnel list	Co-Is were not actively involved in study and roles were replaced by other faculty on campus
	12/14/2020	Added [name] to protocol	[name] is replacing [name] on the protocol.
6	1/26/2021	Increased aim 2 sample size to 40; expanded eligibility criteria to include advanced stage lung cancer patients; added income question to patient baseline questionnaire	Recruitment opportunities have lessened during COVID (patients coming into clinic less often). [name], Co-I, and NCI program officer, [name] were supportive of expanding to advanced stage LC patients given similar treatment and disease characteristics. Increasing sample size to strengthen single arm pilot data and potentially allow for subgroup comparisons to identify ideal eligibility criteria for future trial. Discovered income was erroneously omitted from paper version of patient baseline questionnaire.
7	11/10/2021	Increased aim 2 sample size to 55; added [name] as additional study interventionist	We need 40 evaluable cases (pre-post data) for aim 2 patient-reported outcome analyses. Based on attrition and patients who had to be discontinued, we expect enrolling 55 will yield 40 evaluable cases. [name] is replacing [name] and [name] as a study interventionist, as both are no longer working for the study.

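### Sections 7.2 and 7.3 let missed sessions end study participation, possibly before the post-assessment is due, so non-adherence can become non-retention

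*Combined protocol and SAP*

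**What the plan says.** Section 7.3 (Lost to Follow-Up) applies to a patient who "fails to appear for 3 intervention visits or return an assessment and study staff are unable to contact the participant after at least 3 attempts". Before the label is used, staff try to reschedule the missed session and ask whether the patient wishes to continue. Where possible they telephone three times and check in at an upcoming cancer care visit, and they send a certified letter if necessary. If the patient still cannot be reached, "he or she will be considered to have withdrawn from the study with a primary reason of lost to follow-up".

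Section 7.2 lists the grounds on which an investigator may take a participant off the study. They include loss to follow-up, with a cross-reference to 7.3, and significant non-compliance with the intervention. The second ground carries no condition about being unreachable.

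Section 7.1 treats stopping sessions as distinct from leaving the study: "If a patient discontinues the intervention, but not the study, remaining study procedures will be completed (e.g., post-assessment"). The post-assessment is given at discontinuation if it is due within two weeks, and otherwise at its original date.

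On timing, Section 5.4 states: "Patients will have up to 12 weeks (from the point of their first session) to complete Pathways". Section 4.1 places the post-assessment within 14 days of completing the intervention, and Section 3 places it about 8 weeks after baseline.

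Section 9.4.2 and the analysis plan define retention as "The percentage of patients who complete baseline and post-treatment questionnaires". Adherence is defined separately, as at least 3 of 5 sessions in 10 weeks. Section 3 sets a 70% threshold for each.

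**The concern.** Retention is a question about data: did the patient complete the post questionnaire? Adherence is a question about sessions. A pilot that will inform an efficacy trial needs the two kept apart, because a trial can tolerate patients who skip sessions if their outcomes are still measured.

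The missed-visit limb of 7.3 and the non-compliance ground of 7.2 both let session attendance decide study status. Once a patient is off the study, nothing in either section calls for a T2 attempt when T2 falls due. Section 7.1 has such a provision; 7.2 and 7.3 have no counterpart.

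Three things are at stake. The retention estimate may be lower than the study could have achieved. Retention and adherence may fail in the same patients partly because of the rule and not only because of patient behavior. And the pre-post data, which Section 9.4.3 uses mainly to estimate standard deviations for future studies, may lose the less engaged patients.

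**Working it through.** **1. The plan's own retention figure.** Section 9.2 states that with n = 40 and true retention 0.60, the probability of 19 or fewer retained is below 0.05. The exact binomial gives P(X ≤ 19) = 0.074, so the printed figure is not reproduced. P(X ≤ 18) = 0.039 is below 0.05, and it matches the accompanying rule of more than 21 not retained (40 − 22 = 18). This off-by-one is a separate matter, and the present point does not depend on it.

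**2. Can the missed-visit limb be met before T2?** In the Schedule of Activities (Section 1.2) the five sessions are Visits 2 to 6 and T2 is Visit 7.
- Sessions 2, 3 and 4 missed (Visits 3 to 5): the third miss comes before the last session and before T2. If the contact attempts fail in that interval, the patient is withdrawn before T2 is due.
- Sessions 3, 4 and 5 missed (Visits 4 to 6): the third miss is at the last session. With the 10-day rescheduling period and a clinic check-in, the label may come at or after the T2 date.

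Early withdrawal is therefore possible, but the text does not prescribe it.

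**3. Link to adherence.** Three missed sessions that are not made up leave at most 5 − 3 = 2 completed, below the 3 needed for adherence. The limb is thus reached exactly where adherence has already failed.

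**4. Margin on the retention criterion.** Inputs are N = 55 for feasibility analyses (Section 9.3), the 70% threshold (Section 3), and the version 7 rationale in Section 13: "we expect enrolling 55 will yield 40 evaluable cases".
- Smallest passing count: 0.70 × 55 = 38.5, so 39.
- Planned yield: 40/55 = 72.7%, one above that count.

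| Completers of 55 | Observed | Meets 70%? | Exact 95% CI |
|---|---|---|---|
| 38 | 69.1% | no | 55.2–80.9% |
| 39 | 70.9% | yes | 57.1–82.4% |
| 40 | 72.7% | yes | 59.0–83.9% |

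Each completed T2 moves the estimate by 1/55 = 1.8 percentage points.

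**5. Chance of meeting the criterion.** P(X ≥ 39 | n = 55) is 0.45 at true retention 38/55, 0.68 at 40/55 and 0.87 at 42/55. The step from 40 to 42 assumes two recovered assessments for illustration. The documents give no such number.

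**6. What a changed result would need.** Retention counts questionnaires, not labels. The label matters only for a patient who was withdrawn early and would later have been reached and completed T2. Starting from 40 completers, losing 0 or 1 such patient leaves the criterion met, and losing 2 or more fails it. Starting from 38, recovering 1 meets it.

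**The case against.** A reader might infer that 7.1 and 7.3 contradict each other. They do not. Section 7.1 covers patients who stop the intervention but stay in the study; 7.3 covers patients who cannot be contacted. A patient who silently stops attending and is then reached can be handled under 7.1.

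A reader might also infer that missed sessions alone cause withdrawal under 7.3. The text always requires failed contact as well, and an unreturned assessment is an alternative trigger. The listed efforts are substantial, and Section 5.4 already plans to offer assessments in clinic. A patient missed at the clinic check-in too may not be attending at all, so some of these assessments could never be recovered. All of this stands.

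On size, the forecast of 40 from 55 was itself based on attrition and discontinued patients. It may already include losses under 7.3, and subtracting them again would count them twice. The one-patient margin applies to any cause of a missing T2. Retention is not the primary endpoint, the intervals at 38 and 39 nearly coincide, and the infeasibility rule in Section 9.2 (18 or fewer of 40) is far from this margin. This also stands.

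What the objection leaves in place is the gap itself. The clinic check-in in 7.3 comes before the label and only where possible, and no T2 attempt is required at its due date afterwards. The non-compliance ground in 7.2 reaches even a patient who can be contacted. Section 3 also defines feasibility by the 70% point criterion, so one patient can matter to the stated result.

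**Conclusion.** The point holds as a gap in the follow-up rules that can create avoidable missing T2 data. Sections 7.2 and 7.3 allow session attendance to end study participation, possibly before T2, while 7.1 preserves T2 for patients who stop the intervention.

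The size is not known. At the planned yield the margin is one patient, so a change in the retention result is arithmetically possible. The stronger statement that the rule will change it is not supported: the documents do not say how many patients meet the trigger or how many of those would later complete T2.

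A reader might further infer that the withdrawn label stops the 12-month health-record review. No section says so, and that inference is not part of this point.

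The arithmetic assumes a retention denominator of 55, taken from Section 9.3, because Section 9.4.2 does not state one. It also takes 40 completers from the amendment rationale; both 55 and 40 appear in the current text as well.

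**What to change.** Reconcile 7.1, 7.2 and 7.3 in one amendment:

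- Missed sessions, with or without failed contact, change intervention status only. This applies to the missed-visit limb of 7.3 and to the non-compliance ground of 7.2. Amending 7.3 alone would leave the second route open.
- T2 is still attempted at its scheduled date by the modes already planned (clinic visit, telephone, mail, REDCap), unless the patient has withdrawn from the study or another 7.2 ground applies, such as the participant's best interest.
- Loss to follow-up is declared only when the T2 window closes without an assessment after the attempts listed in 7.3.

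The cost is a short amendment and matching wording in the tracking log. It uses forms and visits already in the plan. The downside is a few more contact attempts and a later date for declaring loss.

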## 8 STUDY ASSESSMENTS AND PROCEDURES

### 8.1 ENDPOINT AND OTHER NON-SAFETY ASSESSMENTS

**Screening.** We will build a separate REDCap project for screening. This screening project will include an eligibility database (i.e., REDCap form) of patients who are screened for eligibility, and a master list database (i.e., separate REDCap form) linking patient names, MRNs, and screening IDs (Appendix K). Because all patients in the study will have an MRN (which includes contact information in it), we will not extract contact information for patients at the screening stage. The eligibility screening database will include patient screener ID, date screened, date must be enrolled by (21 day window), eligibility criteria (e.g., performance status, time on cancer treatment, age, etc.), whether the patient is being rescreened for eligibility, and, if rescreened, the last date of screening (Appendix L). If deemed potentially eligible, additional fields will appear in the eligibility database for tracking dates of upcoming appointments and contact with patients. Patients must be enrolled within 21 days of screening or else they will need to be rescreened.

**Administration of Questionnaires.** Patient-reported measures related to a future efficacy trial and of treatment processes were chosen based on their validity and sensitivity to change in cancer patients and recommendation for clinical trials. These measures will be completed by

patients in both Phase I and Phase II pre-intervention (TP0), during (T1), and post-intervention (TP2) on paper, online (REDCap), or by phone. Patients will use a participation ID on their questionnaires. See **Table 2** for a list of measures to be administered, psychometric properties, assessment schedule, and role in analysis plan. All patient-reported measures will be entered in REDCap (Appendix M, N, O) in the REDCap project built for those patients who enroll.

**Exit Interviews.** Patients participating in Phase I (n = 6) and Phase II (n = 55) of the study will complete an exit interview (Appendix P). The interview will last approximately 15-20 minutes and will query overall satisfaction with the intervention, reactions to the session content, length, and delivery, and assessment relevance. The interviews will take place over the phone or in-person, according to patient preference. Interviews will be conducted by the study team (not the interventionist) and audiorecorded. After each interview, the interviewer will write up observations in the form of field notes (Appendix Q), which will include information about the setting (e.g., details about room if in-person vs. on the phone), personal environment (e.g., respondent's attitude and openness), social environment (e.g., presence of caregiver or others in room), and summary of patient's responses. Recordings will be transcribed verbatim, the transcripts checked for accuracy and deidentified.

**Table 2. Patient-Reported Measures Related to a Future Efficacy Trial**

Construct	Role	Time	Measure	Description
Activity and Role Function	Primary outcome in future trial	T0, T2	PROMIS Satisfaction with Social Roles and Activities 8a Short Form	8 items; Alpha reliability of T-score of 50 = .98; high correlation with well-validated functioning measures.  Recommended for longitudinal research on function in cancer. 
Distress	Secondary outcome	T0, T2	PROMIS Depression Short Form 8a	8 items; Alpha reliability of T-score of 50 = .98. The PROMIS depression measure has been validated for use in cancer patients. 
Purpose	Secondary outcome	T0, T2	PROMIS Meaning and Purpose 4a 	4 items; Assesses one's sense of purpose and that there are reasons for living. Alpha reliability of T-score of 50 = .98.
Hope	Intermediate outcome	T0, T2	State Hope Scale 	6 items; e.g., "I can think of many ways to reach my current goals"; 2 subscales: agency, hope pathways. Good internal consistency in lung cancer patients ( $\alpha = .88$ ). 
Goal Interference	Intermediate outcome	T0, T2	Cancer-Related Goal Interference Scale 	8 items; e.g., "To what extent did the effects of disease/treatment interfere with progress on this project?" Has shown internal ( $\alpha = .90$ ) and concurrent validity. 
Stigma	Intermediate outcome	T0, T2	Lung Cancer Stigma Inventory 	25 items; Assesses internalized, perceived, and constrained disclosure. Correlates with previous measures of stigma used in our studies with lung cancer patients.
Physical Function	Covariate	T0, T2	PROMIS Physical Function Short Form 6	6 items; This measure has been validated in lung cancer patients, with high internal consistency ( $\alpha = .92$ ) and strong correlations with the FACT-G Physical Wellbeing. 
Symptom Severity	Covariate	T0, T2	FACT- Lung Symptom Index 	7 items; Items are an independent subscale of the Functional Assessment of Cancer Therapy – Lung/NCCN Lung Symptom Index. Immunotherapy-specific items used in C1.2 or FACIT system (if available) will be incorporated.

Tobacco use Comorbidity	Covariate	T0	Cancer Patient Tobacco Use Questionnaire  ;	4 items; Assesses lifetime and current tobacco use.
Social Support	Covariate	T0	PROMIS Emotional Support, Instrumental Support V2. 4a;	4 items; Assesses perceived emotional support and instrumental support (e.g., help with tasks).
Demoralization	Secondary outcome	T0, T2	Demoralization Scale –II	16 items; 2 factors: meaning and purpose; distress and coping ability. Patients with low and/or/moderate levels are less likely to have major depressive disorder; those with high levels are more likely to have major depressive disorder.
Care Quality	Secondary outcome	T0, T2	Patient-centered communication in cancer care	8 items; (e.g., To what extent do you and your doctor discuss how cancer is affecting your everyday life?...what is important to you when planning your care?")
Treatment Expectancy	Covariate	T1	HEAL Treatment Expectancy	6 items; Assesses expectations for treatment (e.g., "I am confident in this treatment")
Treatment Receipt	Covariate	T1, T2		7-9 items; (Assesses whether patients perceived that they set goals, discussed values, etc. with the interventionist)
Survey Length		30 minutes based on prior use with this population		

**Review of Existing Data in EHR.** As part of the consent, all patients will be asked to consent to a HIPAA release for permission to collect the following protected health information for up to 12 months post-enrollment:

- age
- gender
- racial and ethnic data
- zip code
- lung cancer diagnosis
- date started lung cancer treatment
- comorbidities (other health conditions)
- type of cancer treatments received and dates received
- types of other services received for cancer care and dates received
- response to cancer treatment
- dates of hospitalizations and reasons hospitalized
- referrals to services for cancer care
- documentation of advance care planning
- date of death, place of death (hospital, home)

This information will be collected by study staff and entered in REDCap or obtained through clinical informatics service.

